8.2. Primary Analysis for OS

The primary analysis for estimating the hazard rate for the time to OS denoted as the function $S(t)$ will be performed on the PP population using the Kaplan Meier (KM) Product-Limit estimation method. A secondary analysis will also be implemented for the FAS. Using the KM method:

- The median survival time along with the 95% Confidence Interval (CI) will be constructed.
- The 25Th and 75th quartile of survival time will also be provided supplemented by the Kaplan-Meier plot of OS.

8.2.1. Assumption Testing

No assumption check is planned for the Kaplan-Meier method.

Patient Characteristic Subgroup Factors

Among the patient factors to be explored are the following patient derived variables.

Age category

- <65 vs ≥ 65

Gender

- Female vs Male

MGMT

- unmethylated vs methylated

Hispanic or Latino

- yes=1 vs no=0

Race

- White vs not White

IDH

- wild-type vs mutated

Prior Steroid

- yes=1 vs no=0

Enhanced Lesion

- unifocal vs Multifocal

Number of Lesions at Entry

- 1 vs > 1

KPS Screening, N (%)

- ≥ 70 to 90 vs ≥ 90

veledimex Dosing Compliance

- $<100\% (<80\%)$ vs $100\% (\geq 80\%)$

8.2.3. Estimation of OS using Parametric Survival Assumptions for S(t)

In addition to estimating S(t) based on the KM method, S(t) will be estimated under the assumption that S(t) is Weibull distributed for shape and scale parameters to be explored.

8.3. Secondary Efficacy Endpoints

All secondary endpoint determination related to tumor assessment is based on the investigator assessment. If applicable an independent review committee (IRC) will also perform tumor response and tumor progression assessments based on the methods of tumor assessment defined in the IRC charter. Secondary endpoints for estimation include:

8.3.1. The OS rate at fixed timepoints 6, 12, 18 and 24 months

- OS rates will be derived from the KM estimate along with the corresponding two-sided 95% CI estimated using Greenwood's formula for the variance and the log-log transformation applied to the survivor function S(t)

8.3.2. Overall PFS and PFS rate at fixed timepoints 6, 12, 18 and 24 months

- Overall PFS and the PFS rate of pseudo-progression (PSP) will also be estimated. at month 6, 12, 18 and 24 with corresponding 95% confidence interval (CI).

PFS is defined as the duration of time from the first dose of study drug (i.e., cemiplimab at Day -7) to the confirmed progression (as determined by immunotherapy Response Assessment for Neuro Oncology (iRANO) criteria) or death from any cause, whichever occurs first. Censoring will be considered as below:

- Subjects who discontinue study without any event will be censored at date of discontinuation.
- Subjects who are lost to follow-up without any event will be censored at last follow-up contact date.
- If the subject has no progression or not died, the subject is censored if still alive up to 2 years from the first dose of study drug received.

The time to PFS will be estimated on the PP population using the Kaplan Meier (KM) Product-Limit estimation method. The median PFS will be summarized along with corresponding 95% CI. A Kaplan-Meier plot of PFS will also be provided.

Pseudo-progression (PSP) is a term used to describe the appearance of radiographic disease progression due to increase contrast enhancement on MRI without true tumor progression. The increase in contrast enhancement can be influenced by several parameters including differences in radiologic technique, the amount of contrast agent used, the timing of the contrast agent administration relative to the imaging, postsurgical changes, infarction, treatment related inflammation, seizure activity, sub-acute radiation effects, radiation necrosis, and corticosteroid use. Consideration of these factors by experts and clinical experience is likely to identify these subjects.

Number and proportion of subjects with PSP will be summarized with corresponding two-sided 95% confidence interval (CI).

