16.3.2. Secondary Endpoints

Secondary endpoints include:

- Overall survival rate will be determined at 6, 12, 18 and 24 months
- PFS, and rate of pseudo-progression (PSP) of Ad-RTS-hIL-12 + veledimex when administered in combination with cemiplimab-rwlc
- ORR of Ad-RTS-hIL-12 + veledimex when administered in combination with cemiplimab-rwlc at 6, 12, 18 and 24 months
- Tumor response rate of Ad-RTS-hIL-12 + veledimex when administered in combination with cemiplimab-rwlc at 6, 12, 18 and 24 months

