8.1. Primary Efficacy Endpoint

The primary endpoint for evaluation of efficacy is the OS hazard rate which is performed by estimating the hazard rate based on the accrual and follow-up of all treated subjects. Subjects will be followed from the first date of treatment up to 2 years for overall survival.

OS is defined as the duration of time from the first dose of study drug (i.e., cemiplimab at Day - 7) to the date of death from any cause. Censoring will be considered as below:

- Subjects who discontinue study will be censored at date of discontinuation.
- Subjects who are lost to follow-up will be censored at last follow-up contact date.
- If the subject has not died, the subject is censored if still alive up to 2 years from the first dose of study drug received.

All summaries and analyses for the primary efficacy endpoint will be based on per-protocol population.

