Table 14.2.1.1	Objective Response Rate	Per Protocol Population	ORR					
Table 14.2.1.2	95% Confidence Intervals for Overall Response	Per Protocol Population	ORRci					
Table 14.2.2	Progression Free Survival	Per Protocol Population	PFS					
Table 14.2.3	Time to Overall Survival in Months	Per Protocol Population	OS			SS	ADTTE	
Table 14.2.3.1	OS for 20mg group 1 main study and 20 mg expansion for patients characteristics subgroups	Per Protocol Population	OSCAT					

Table 14.3.1.1	Overall TEAEs Summary	Full Analysis Population	AEoverall			AE	ADAE	AeOverall is done
Table 14.3.1.2	Treatment Emergent Adverse Events by System Organ Class and Preferred Term	Full Analysis Population	AEs			AE	ADAE	AEs tables are done
Table 14.3.1.3	Treatment-Related Adverse Events by System Organ Class and Preferred Term	Full Analysis Population	AEs			AE	ADAE	AEs tables are done
Table 14.3.1.4	Adverse Events Leading to Study Discontinuation by System Organ Class and Preferred Term	Full Analysis Population	AEs			AE	ADAE	AEs tables are done
Table 14.3.1.5	Adverse Events Leading to Discontinuation of Study Medication by System Organ Class and Preferred Term	Full Analysis Population	AEs			AE	ADAE	AEs tables are done
Table 14.3.1.6	Adverse Events Leading to Interruption of Study Medication by System Organ Class and Preferred Term	Full Analysis Population	AEs			AE	ADAE	AEs tables are done
Table 14.3.1.7	Adverse Events Leading to Dose Reduction of Study Medication by System Organ Class and Preferred Term	Full Analysis Population	AEs			AE	ADAE	AEs tables are done

Table 14.3.1.8	Adverse Events Leading to Death by System Organ Class and Preferred Term	Full Analysis Population	AEs			AE	ADAE	AEs tables are done
Table 14.3.1.9	Treatment Emergent Adverse Events by System Organ Class, Preferred Term and Severity	Full Analysis Population	AEs			AE	ADAE	AEs tables are done
Table 14.3.1.10	Treatment Emergent Adverse Events by System Organ Class, Preferred Term and Severity with CTCAE Toxicity Grade ≥ 3	Full Analysis Population	AESev			AE	ADAE	AESev tables are done
Table 14.3.1.11	Serious Adverse Events by System Organ Class and Preferred Term	Full Analysis Population	AESev			AE	ADAE	AESev tables are done
Table 14.3.1.12	Treatment Emergent Adverse Events by Preferred Term in Decreasing Frequency	Full Analysis Population	AEPT			AE	ADAE	AEPT tables are done

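### PFS is censored by the overall-survival rules (discontinuation, last contact, alive at 2 years) and not at the last tumour assessment, so any PFS estimate is biased upward when MRI stops before contact does

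*SAP*

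**What the plan says.** SAP 8.3.2 sets the start and the event: "PFS is defined as the duration of time from the first dose of study drug (i.e., cemiplimab at Day -7) to the confirmed progression", by iRANO, or death from any cause if earlier. It then gives three censoring rules:

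- A subject who leaves the study with no PFS event is censored on the day of leaving.
- On loss of contact, the rule is "Subjects who are lost to follow-up without any event will be censored at last follow-up contact date".
- For those still under observation, the wording is "If the subject has no progression or not died, the subject is censored if still alive up to 2 years from the first dose". This rule gives no censoring date; 2 years is the natural reading.

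The OS rules in SAP 8.1 are the same three. The loss-to-follow-up rule there reads "Subjects who are lost to follow-up will be censored at last follow-up contact date".

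Neither document has a PFS rule based on the last tumour assessment, on missed scans or on new anticancer therapy. SAP 8.3.5 does stop at new anticancer treatment, but only for best overall response.

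Protocol 13.1 and 13.2 plan the first response MRI at Day 57, then every 8 weeks for 2 years until progression is confirmed.

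On the status of the analysis, SAP 10.1 and 10.2.3 remove overall PFS and the PFS rates from the final analysis. The SAP appendices hold two TLF lists. One marks the table titled "Progression Free Survival" as not needed for now; the other carries it without that note. Both keep Kaplan-Meier figures for PFS and a PFS data listing. PFS is still a secondary endpoint in Protocol 16.3.2 and SAP 3.3.2.

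**The concern.** For OS, a contact date is the right censoring date, because contact establishes survival. For PFS it is not, because progression is identified on MRI. Under the rule as written, the interval between the last scan and the last contact is treated as observed progression-free time.

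The protocol leaves room for such an interval. Section 16.6.2 says that after a discontinuation event, which includes symptomatic deterioration, the subject is followed only for OS. Section 17.4 instead asks that subjects who stop treatment without progression be followed until progression is confirmed. Survival status and new therapies are tracked for 2 years. A subject can therefore be known to be alive while no longer being scanned.

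The trial has one arm, and its estimates are to be set beside historical controls (Protocol 16; SAP 8). No concurrent arm shares the bias, so an upward shift in PFS would look like benefit.

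**Working it through.** **The plan's own figures.** The documents give no PFS event count, power or expected rate, so there is nothing to reproduce for PFS. As a yardstick, the stated standard error of at most about 10% for an OS rate does reproduce: √(0.5 × 0.5 / 25) = 0.10. At a PFS rate of 20% it is √(0.2 × 0.8 / 25) = 0.08, and at 4% it is √(0.04 × 0.96 / 25) = 0.039.

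**Scan times.** Day 57 is 64 days after Day -7. With 30.4375 days per month (SAP 11.5), scans fall at 64, 120, 176 and 232 days, or 2.10, 3.94, 5.78 and 7.62 months. The last scan before 12 months is at 344 days, or 11.30 months.

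**Mechanism by hand.** Kaplan-Meier: S(t) = product of (1 − d/n). Take 25 subjects, of whom 10, 6, 4 and 2 progress at the first four scans. The other 3 are scanned at Day 57, never again, and are alive at 2 years.

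- As written (3 censored at 24 months): 6-month PFS = 15/25 × 9/15 × 5/9 = 20%; 12-month PFS = 20% × 3/5 = 12%.
- Censored at the last MRI: 6-month PFS = 15/25 × 6/12 × 2/6 = 10%; 12-month PFS = 10% × 0/2 = 0%.

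This shows only what the rule does with three unscanned survivors. Their true progression status is unknown.

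**Simulation inputs.** Protocol 6.1 gives a median PFS of 2 to 3 months and a median OS of 6 to 7 months in recurrent disease. The values used are 2.5 months to progression and a further 4 months to death (2.5 + 4 = 6.5), with exponential times. First detection on a scan is taken as the progression event, without the 12-week confirmation. The share of subjects event-free at the first scan who then stop MRI is an assumption: 0%, 10%, 20% or 30%.

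**True values.** With complete imaging, 6-month PFS is close to 2^(−5.78/2.5) = 0.201 and 12-month PFS close to 2^(−11.30/2.5) = 0.044. The simulation gives 20% and 4.2% to 4.3%.

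**As written, stoppers still followed for survival.** At 10/20/30% stopping, 6-month PFS is 22/25/27% and 12-month PFS is 6/8/9%. If stoppers are instead lost to contact within the following 12 months, the inflation is smaller: about 5% at 12 months with 10% stopping. At 0% the rules agree to within 0.1 point.

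**What each remedy does, at 20% stopping (12-month PFS):**

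| Stoppers are | As written | Last MRI for event-free subjects | Last MRI plus missed-scan rule |
|---|---|---|---|
| lost to contact | 6.1% | 4.1% | – |
| followed for survival | 7.6% | 7.1% | 4.1% |
| treated as study discontinuers within 8 weeks of the last scan | 4.2% | – | – |

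The true value is 4.2% to 4.3%. In the second row most of the bias comes from deaths that replace an earlier, unseen progression. Moving only the event-free survivors back to the last MRI leaves those late deaths in place.

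**The case against.** Three objections carry weight.

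**The first rule may already catch the problem.** If a subject who stops scanning counts as having discontinued the study, PFS is censored at about that date and the bias disappears (third row of the table). A reader might infer that anyone unscanned after Week 8 but alive at Month 24 is always counted as progression-free for 24 months. The documents do not support that, since it applies only to subjects not classed as discontinued. The rule is not a full answer, however. SAP 8.1 censors OS on the same event, so a wide reading that rescues PFS would also cut off the OS follow-up that Protocol 16.6.2 says continues.

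**The analysis has been withdrawn.** A reader might infer that the trial's final report will carry an inflated PFS. SAP 10.2.3 says otherwise. The TLF lists may simply be out of date, since they also keep vital-sign and ECG tables that Section 10.6 drops. This limits the consequence. It does not correct the rule, and any PFS curve produced from those lists would use it.

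**The size is assumed.** No document gives a rate of early MRI stopping, and with scans on schedule the effect is nil. It would be too strong to say that the bias always favours the treatment. Most of the differences are also smaller than the standard error at 25 subjects. They are systematic, though, and a confidence interval does not reflect them.

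Censoring at new anticancer therapy is a choice of estimand. Its absence is not in itself an error.

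**Conclusion.** The point holds in a limited form. The PFS censoring rules in SAP 8.3.2 are OS rules, and they bias PFS upward whenever MRI stops before contact does.

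Under assumed stopping of 10% to 30%, the inflation is about 2 to 7 points at 6 months (22% to 27% against 20%) and about 1 to 5 points at 12 months (5% to 9% against 4%). These figures rest on the median times taken from Protocol 6.1, on exponential times, and on stoppers not being classed as study discontinuers. With no early stopping there is no effect.

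Because SAP 10.2.3 drops PFS from the final analysis, what is at stake is the PFS figures, listing and table still in the TLF lists, and any later analysis of this secondary endpoint. The primary OS analysis is not affected by this point. The rule should be corrected, but it does not threaten the trial's main conclusion.

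**What to change.** In SAP 8.3.2:

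- Censor event-free subjects at the last adequate MRI, or at first dose if there is no post-baseline MRI.
- When death or progression follows two or more consecutive missed scans, censor at the last adequate MRI before the gap. Without this rule, most of the bias remains when later deaths still count.
- Keep contact-date censoring for OS only.
- Report censoring at new anticancer therapy as a sensitivity analysis.
- Reconcile Section 10.2.3 with the PFS table, figures and listing in the TLF lists, either by removing them or by stating that they follow the corrected rule.

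The cost is SAP wording and modest programming, since MRI results and new therapies are already collected. PFS follow-up becomes slightly shorter, with fewer events. The missed-scan rule can itself be mildly informative: in the simulation, removing late deaths in this way gives 6-month PFS of 18% to 20% against a true 20%.

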8.3.3. Objective Response Rate (ORR) at 6, 12, 18 and 24 months

The ORR, determined according to Recist 1.1 confirmed response criteria instead of iRANO criteria will be summarized at month 6, 12, 18 and 24 with corresponding two-sided 95% confidence interval (CI).

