13. TUMOR RESPONSE ASSESSMENTS

13.1. Tumor Response

The secondary time-to event endpoints of this study include Investigator assessment of PFS, and ORR.

Tumor response will be evaluated radiographically using MRI scans to determine tumor response and to assess the time of objective disease progression (estimate of PFS). A baseline MRI should be performed within 24 hours (a + 48hr window is allowed) of Ad-RTS-hIL-12 administration. The Ad-RTS-hIL-12 injected lesion and/or other measurable brain lesions will be measured according to the iRANO criteria guidelines attached in [Appendix 4](#). MRI scans will be collected and stored at the study site and each subject will be evaluated for response by the study investigator. Subjects should be imaged throughout the study using the same method(s) as were used for the screening and baseline MRIs. Independent tumor response assessments, as well as posttreatment tumor biopsies, may occur as available and at the discretion of the investigator. A repeat scan to confirm progression should be completed at 12 weeks (per iRANO) after first documentation of progression. Consideration should be given to performing a diagnostic brain biopsy, which should be performed in accordance with the current iRANO guidelines.

Tumor response will be assessed both locally and at an independent central imaging lab using the iRANO criteria. Copies of all scans will be provided to the independent central imaging lab for determination of tumor response. Final progression determinations will be made by the independent central imaging lab. Every effort should be made to continue study therapy until disease progression is confirmed per iRANO criteria. In the instance that a subject is withdrawn from study treatment due to investigator determined progression, scans should be obtained and provided to the central imaging lab until disease progression is confirmed centrally.

Response is defined by radiographic and clinical criteria. Complete response (CR) or partial response (PR) will be first assessed by radiographic changes that indicate a reduction of bidimensional tumor size as per iRANO criteria. In addition, changes in neurologic function and steroid use will be considered to determine stable disease (SD).

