16.6.4. Tumor Response Analyses

Investigator assessment of ORR and PFS will be determined according to iRANO criteria. A two-sided confidence interval will be computed for the ORR. PFS and OS will be estimated using the Kaplan-Meier method for appropriately-sized subject groups.

Following completion of the study, best response will be determined for each subject in accordance with iRANO guidelines and the ORR will be presented for all subjects. Where applicable, summary data of PFS, OS, and durability of response will be determined using Kaplan-Meier methodology; otherwise, a listing by-subject will display the data obtained. Two-sided confidence intervals will be computed for the ORR. Descriptive statistics will be performed for different patient populations.

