3.4. Treatments

The current plan for the Phase II study in glioblastoma is to begin dosing with:

- Cemiplimab (Libtayo®) at 350 mg Intravenously (IV) on day -7 (± 3 days), then again on day 15 and then on:
 - Day 36 (± 3 days), Day 57 (± 3 days),
 - then subsequently for every 3 weeks (Q3W ± 7 days) until confirmed progression (iRANO), unacceptable toxicity or subject withdrawal.
- On Day 0 (day of Ad-RTS-hIL-12 administration) subjects will take one dose of veledimex 3 \pm 2 hours prior to injection of Ad-RTS-hIL-12 and Ad-RTS-hIL-12 [REDACTED] will be administered by freehand injection.
 - After tumor resection and Ad-RTS-hIL-12 injection, veledimex will be administered orally for 14 days. The first post-resection veledimex dose is to be

given on Day 1. Subsequent veledimex doses are to be taken once daily, in the morning and within approximately 30 minutes of a regular meal. The first veledimex dose following Ad-RTS-hIL-12 injection is expected to be administered when the subject is at the clinical site, under careful medical supervision by the clinic staff to ensure that the subject does not have difficulty swallowing the capsules.

- Thereafter, subjects may be allowed to self-administer the remaining once daily doses as described. Subjects are to be instructed to take the appropriate number of capsules in the same way for each of the remaining treatment period days and may be reminded to do so by phone on non-visit days.
- Subjects should NOT make up any missed doses.
- Subjects should be instructed to document veledimex dosing compliance in a subject diary, including the time subject took the once daily dose, the time subject ate breakfast, the number of capsules taken, whether subject missed any veledimex doses, and the study day and reason for any missed doses. Study drug container(s) with any remaining capsules should be returned to the study staff on Day 15, so that staff can properly assess dose compliance.

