8.3.4. Tumor Response Rate

- Determination of tumor response will be performed on each subject in the PP population.
- The Tumor response rate of Ad-RTS-hIL-12 + velevidemex when administered in combination with cemiplimab will be estimated at 6, 12, 18 and 24 months.
- Tumor response will be defined by radiographic and clinical criteria. Complete response (CR) or partial response (PR) will be first assessed by radiographic changes that indicate a reduction of bi-dimensional tumor size as per Recist 1.1 criteria. In addition, changes in neurologic function and steroid use will be considered to determine stable disease (SD).

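### SAP 8.3.3 and 8.3.4 score tumour response by RECIST 1.1 where the protocol and SAP PFS use iRANO, with no reason or conversion rule, and the SAP leaves open whether ORR is still reported

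*SAP*

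**What the plan says.** **Protocol.** Section 16.6.4 states: "Investigator assessment of ORR and PFS will be determined according to iRANO criteria". Section 13.1 defines complete and partial response through a "reduction of bidimensional tumor size as per iRANO criteria", and adds neurologic function and steroid use when stable disease is determined. The MRI footnote to Table 1 has target lesions selected and measured under iRANO. The synopsis requires at least 20 subtotal resections so that enough subjects have disease measurable for iRANO response.

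**SAP, response.** Section 8.3.3 has ORR "determined according to Recist 1.1 confirmed response criteria instead of iRANO criteria". Section 8.3.4 bases complete and partial response on "a reduction of bi-dimensional tumor size as per Recist 1.1 criteria".

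**SAP, progression and treatment.** Section 8.3.2 defines the PFS event as confirmed progression "as determined by immunotherapy Response Assessment for Neuro Oncology (iRANO) criteria", or death. Section 3.4 continues cemiplimab "until confirmed progression (iRANO), unacceptable toxicity or subject withdrawal".

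**SAP, status of these analyses.** Sections 10.1 and 10.2 remove PFS, ORR, tumour response rate and best overall response (BOR) from the final analysis, because the study report is now abbreviated. Sections 4.5.3 and 4.7.1 still assign ORR to analysis populations. Both table lists in the appendices still contain a table titled "Objective Response Rate" and one for its confidence interval.

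**The concern.** Response is a secondary endpoint, and the protocol fixes the rule by which it is read. A different rule in the SAP makes the reported ORR a different quantity from the one the protocol defined. It also leaves response and progression in the same subject read under two named systems.

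The change comes without a rationale in a SAP that already describes 40 treated subjects in the database of an uncontrolled, single-arm study. In that setting a reader will want to know why the rule changed.

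There is a practical problem as well. A programmer given 8.3.4 has a bi-dimensional measure attributed to RECIST 1.1, lesion data collected under iRANO, and no instruction for getting from one to the other.

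**Working it through.** The plan states no figure that depends on the response criterion, so there is none to reproduce. The check is a comparison of the texts, followed by a small calculation of sensitivity.

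**Step 1. Which criterion applies where**

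| Item | Protocol | SAP |
|---|---|---|
| Lesion selection and measurement | iRANO (Table 1, MRI footnote) | no separate rule |
| Complete/partial response | iRANO, bidimensional (13.1) | RECIST 1.1, bi-dimensional (8.3.4) |
| ORR | iRANO (16.6.4) | RECIST 1.1, confirmed (8.3.3) |
| BOR | iRANO (16.6.4) | best investigator response on the eCRF, no criterion named (8.3.5) |
| PFS event | iRANO (16.6.4) | iRANO-confirmed progression or death (8.3.2) |
| Continuing cemiplimab | iRANO (synopsis) | iRANO (3.4) |

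Within the SAP, only ORR and tumour response have moved to RECIST 1.1. That the two systems differ needs no outside source, since 8.3.3 itself presents one as a replacement for the other.

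**Step 2. Can 8.3.3 and 8.3.4 be carried out as written?** Section 8.3.4 follows the protocol's definition of response closely, with the name of the criterion changed. It keeps the bi-dimensional measure and the use of neurologic function and steroid use for stable disease. SAP 8.3 takes tumour endpoints from the investigator's assessment, which the protocol has made under iRANO. SAP 4.4 reports that the imaging data objective was put on hold and not performed, so no central read is described there that would supply RECIST responses. No derivation rule is given in either section.

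**Step 3. Is ORR in or out of the final analysis?**
- Out: SAP 10.1 and 10.2.4, with tumour response (10.2.5), BOR (10.2.6) and PFS (10.2.3).
- In: SAP 4.5.3 (per-protocol population) and 4.7.1 (per-protocol, with the full analysis set as secondary).
- In: both table lists carry Tables 14.2.1.1 (ORR) and 14.2.1.2 (confidence intervals). In the first list the PFS table is marked as not needed for now; the ORR and BOR tables have no such mark.

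The SAP does not say which of these governs. If the ORR tables are run, 8.3.3 is the only rule the SAP gives for ORR.

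**Step 4. How much one reclassified subject matters**
- Change in ORR per subject = 1/n. At n = 25 (planned evaluable number): 1/25 = 4.0 points. At n = 20 (the subtotal-resection minimum): 1/20 = 5.0 points.
- Illustration with assumed counts and exact (Clopper-Pearson) 95% intervals: 2/25 = 8% (1.0% to 26.0%); 4/25 = 16% (4.5% to 36.1%).

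These figures show sensitivity only. The number of subjects who would change category cannot be obtained from the documents, which reproduce neither set of thresholds and contain no lesion data.

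**The case against.** The strongest reply is that SAP 10.2 withdraws both sides of the conflict. Section 8 sends the reader to Section 10 for changes, and 10.2 removes the RECIST-based ORR and the iRANO-based PFS alike. A reader might infer from 8.3.2 to 8.3.4 that two conflicting rules will be reported side by side; on 10.2 as written, neither analysis is planned. This stands and limits the impact.

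The table lists are also weak evidence of intent. They still carry vital-sign and ECG tables that 10.6 drops, and plots by veledimex dose although the trial uses a single 20 mg dose. In the second list the ORR, BOR and PFS rows have no source datasets entered, whereas overall survival does. That stands too, although the dataset entries are no sure guide: the ECG tables, which 10.6 drops, have them. The lists do not prove that ORR will be produced. Together with 4.5.3 and 4.7.1, they show that the SAP does not settle the question.

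Three stronger readings are tempting and not supported.
- **A subject shown to be a responder under one rule and a progressor under the other.** Suppose, as an assumption, that one rule uses the product of two diameters and the other the longest diameter. A lesion going from 40x30 mm to 40x15 mm falls from 1200 to 600 mm² by product (50%) and stays at 40 mm by longest diameter (0%). No change is not progression, and the documents give no thresholds.
- **The protection against miscalling pseudo-progression is removed.** SAP 8.3.2 defines PFS by iRANO-confirmed progression and describes a separate pseudo-progression summary, and SAP 3.4 keeps iRANO for continuing treatment.
- **The BOR tables carry RECIST 1.1.** Section 8.3.5 names no criterion, and the investigator's response it relies on is an iRANO response under the protocol.

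Finally, the switch is disclosed in the SAP, as Protocol 16.6.8 asks of deviations, and no hypothesis test depends on it. It is unexplained, not concealed.

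**Conclusion.** The point holds in a limited form. SAP 8.3.3 and 8.3.4 replace the protocol's response criterion without a reason or a conversion rule, 8.3.4 attaches a bi-dimensional measure to RECIST 1.1, and PFS stays on iRANO. Any ORR table produced under this SAP would not be the protocol's ORR.

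The consequence depends on whether ORR is reported. If 10.2 governs, this is an error of wording in a withdrawn analysis. If 4.5.3, 4.7.1 and the table lists govern, the reported ORR changes definition, by 4 points for each subject reclassified out of 25. How many that would be is unknown.

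The conclusion rests on the text of the two documents and on the SAP's own treatment of the criteria as alternatives. It does not rest on any assumed threshold, and it says nothing against the primary endpoint, overall survival.

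**What to change.** 1. In SAP 8.3.3 and 8.3.4, replace RECIST 1.1 with iRANO, as in Protocol 13.1 and 16.6.4. This also makes the bi-dimensional wording in 8.3.4 correct.
2. In SAP 8.3.5, state that BOR uses the investigator's iRANO response.
3. If RECIST 1.1 is wanted, present it only as a labelled sensitivity analysis, with the reason and a rule for deriving it from the lesion measurements collected.
4. Align SAP 10.2 with 4.5.3, 4.7.1 and both table lists, so that ORR, tumour response, BOR and PFS are each clearly in or out.

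The cost is SAP wording and a pass through the table lists. No new data collection is needed for the iRANO version: listings of target, non-target and non-enhancing lesions, overall response and corticosteroid dosage are already planned. A RECIST sensitivity analysis would add the work of writing and programming its derivation.
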